1.4.3 Rationale for Treatment Combination

1.4.3.1 Nonclinical Data Obinutuzumab and Atezolizumab

As presented in Section 1.2.1, nonclinical xenograft experiments consistently demonstrated superiority of obinutuzumab over rituximab.

Obinutuzumab and atezolizumab have complementary mechanisms of action, acting at different steps of the anti-tumor immune response. Obinutuzumab induces direct tumor-cell killing with subsequent release of tumor antigens for immune presentation (immunogenic cell death). Additionally, obinutuzumab was engineered to augment antibody-dependent cellular cytotoxicity, resulting in enhanced binding to Fc γ RIIIA/B (CD16a/b). Thus, obinutuzumab has the ability to enhance T-cell priming and immune-cell activation through interactions with NK cells, T cells, monocytes/macrophages, dendritic cells, and neutrophils cells carrying Fc γ RIIIA or Fc γ RIIIB. Atezolizumab affects primarily the effector phase of the immune response by restoring cytotoxic T-cell function.

Studies of obinutuzumab plus atezolizumab have not been performed in nonclinical murine models because there are no suitable models for testing the combination. However, synergism was exhibited when the combination of a surrogate anti-mouse PD-L1 antibody, and an anti-mouse CD20-depleting antibody was tested using a syngeneic A20 lymphoma model in immune-competent mice (see Section 1.3.1). Although the anti-CD20 agent used in this study is not completely identical to obinutuzumab, the results provide compelling proof of concept for exploring this combination in clinical trials.

Lenalidomide

Lenalidomide, a thalidomide analogue, is a potent immunomodulatory agent with activity in lymphoid malignancies occurring primarily through immune modulation and direct anti-tumor effects. Currently, lenalidomide is approved for the treatment of multiple myeloma, deletion 5q myelodysplastic syndromes, and mantle cell lymphoma.

Nonclinical studies demonstrated that T-cell immune synapse dysfunction in FL can be restored with lenalidomide (Ramsay et al. 2009). In addition, lenalidomide has been shown to reduce T regulatory cells and activate CD8 T cells (Kater et al. 2014). E3 ligase protein cereblon (encoded by the CRBN gene) is the molecular target of lenalidomide. Lenalidomide binding to CRBN mediated its direct anti-tumor effects and is also required for T-cell production of interleukin-2 (IL-2) and tumor necrosis factor α (Lopez-Girona et al. 2012).

In nonclinical studies, lenalidomide combined with rituximab resulted in anti-tumor effects via increased NK cell function, enhanced antibody-dependent cell-mediated cytotoxicity, and improved NK cell-mediated synapse formation (Wu et al. 2008; Zhang et al. 2009).

The combination of obinutuzumab with lenalidomide has been evaluated in nonclinical studies using the mantle cell lymphoma Z138 xenograft model in severe combined immunodeficient-beige mice. Results from these studies demonstrated greater anti-tumor efficacy than either drug as a single agent and superior activity to the combination of lenalidomide with rituximab (data available on request [RDR 1064289]).

1.4.3.2 Available Clinical Data

BO29562 is the only study currently evaluating the combination of atezolizumab, obinutuzumab, and lenalidomide in lymphoma.

A Phase Ib study of atezolizumab in combination with obinutuzumab in patients with relapsed or refractory FL and DLBCL (Study GO29383) is currently in progress, sponsored by Roche. Preliminary results indicated that atezolizumab combined with obinutuzumab is well tolerated with evidence of clinical activity in this patient population (Palomba et al. 2016). A total of 49 patients were enrolled and dosed: 26 with FL and 23 with DLBCL. The doublet combination appears to be safe and tolerable, and is consistent with what has been observed with the respective single agents and the diseases under study. As of the 14 June 2017 data cutoff, a review of safety data in GO29383 in FL (n=26) and DLBCL (n=23) did not reveal any new safety signals. The most commonly reported (>20%) treatment-emergent adverse events included the preferred terms (PTs): fatigue, pyrexia, nausea, diarrhea, abdominal pain, cough, and decreased appetite. The most common Grade 3–4 treatment-related adverse events were neutropenia (8%), diarrhea (8%), and pain (8%). There were no adverse events with fatal outcomes reported in FL. Atezolizumab + obinutuzumab demonstrated encouraging signs of response in heavily pretreated and refractory patients with relapsed/refractory FL. The ORR at the end of induction assessment (Lugano 2014 Response Criteria by PET-CT) was 56.5%, with a CR rate of 26.1%. The median duration of response and median PFS at time of clinical cutoff were 15.0 and 15.1 months, respectively. Although preliminary, these data may support the hypothesis that the addition of obinutuzumab to atezolizumab has the potential to reduce the incidence of autoimmune side effects observed with atezolizumab monotherapy by depleting B cells.

Clinical activity of lenalidomide has been demonstrated in the treatment of both relapsed or refractory indolent and aggressive NHL as a single agent (Wiernik et al. 2008; Witzig et al. 2011) and in combination with rituximab (see Section 1.1).

Obinutuzumab in combination with lenalidomide is currently being evaluated in an ongoing Phase Ib/II study sponsored by the Lymphoma Academic Research Organisation (Study MO28005 [GALEN]) in patients with relapsed or refractory FL and aggressive lymphoma (DLBCL and mantle cell lymphoma), and supported by Roche in the form of an investigator-initiated study model. The recommended dose of lenalidomide was established at 20 mg/day on the basis of an increased incidence of Grade 3 or 4 neutropenia between Cycles 2 and 6 at the next higher dose of 25 mg/day

(Morschhauser et al. 2014). The most common (occurring in $\geq 20\%$ patients) adverse events observed during the dose escalation phase (all grades) in the 19 patients were neutropenia and constipation (10; 53% each), asthenia and upper respiratory tract infection (7; 37% each), rash/cutaneous eruption and cough (5; 26% each), and diarrhea and fever (4; 21% each). The only Grade 3 or 4 adverse event that occurred in 2 or more patients was neutropenia (8/19; 42%). IRRs occurred in 3 patients and did not exceed Grade 2. Preliminary efficacy data available from the dose-escalation phase of the study are encouraging, with an overall response according to Cheson 1999 criteria of 68% (13 of 19 evaluable patients), including 7 patients with a CR; 3 patients with a CR, unconfirmed; and 3 patients with a PR (Morschhauser et al. 2014).

The Phase II portion of the GALEN study is currently ongoing. Data for the 89 patients enrolled in the relapsed/refractory FL cohort (cutoff date: 22 November 2016) were presented at the 14th ICML conference (Morschhauser et al. 2017). The expansion phase at 20 mg/day of lenalidomide for the first-line FL cohort is currently in progress. Eighty-eight patients with relapsed/refractory FL were evaluable for safety and 86 for efficacy. With a median follow-up of 18.1 months, 75 patients (87.2%) completed induction and 67 (78%) entered maintenance. The median induction treatment duration was 5.3 months (0.2–6.7), with a median number of cycles received of 5.4 (1–6). The median dose intensity for both drugs was $>98\%$ during induction.

Preliminary results from the GALEN study suggest that the addition of lenalidomide to obinutuzumab represents an effective and safe combination in patients with relapsed or refractory FL. The overall response according to Cheson 2007 criteria was 74% (CR/CRu rate of 44%) and the 1-year PFS rate was 75.5% (95% CI: 64.2–83.7). The most common adverse events ($>20\%$ of patients) during induction (all grades) were gastrointestinal disorders (76%), infections (63%), asthenia (52%), neutropenia (31%), muscle spasms (30%), and cough (21%). The most common Grade 3/4 adverse events were infections (7%) and neutropenia (28%). Febrile neutropenia occurred in 3.4% of patients. Six second primary malignancies were reported in 3 patients (5 basal carcinoma and 1 myelodysplastic syndrome), and there were 3 fatal adverse events reported (3.4%): febrile neutropenia, pneumonia, and atypical pneumonia.

Currently available data continue to provide a strong rationale for an improved benefit–risk ratio with the addition of atezolizumab to the combination of obinutuzumab and lenalidomide in patients with FL. Strengthening the immunotherapy component of the combination is expected to result in deeper and long-lasting anti-tumor responses. Additionally, overlapping toxicities are expected to be manageable in the clinical setting and drug–drug interactions (DDIs) are unlikely to occur (see Section 5.1.4).

2. OBJECTIVES AND ENDPOINTS

This study will evaluate the safety, efficacy, pharmacokinetics, and immunogenicity of induction treatment consisting of atezolizumab in combination with obinutuzumab plus lenalidomide (Atezo+G+Len) in patients with relapsed or refractory FL, followed by maintenance treatment with Atezo+G+Len in patients who achieve a CR, a PR, or stable disease at EOI (see Section 3.1 for details). Specific objectives and corresponding endpoints for the study are outlined below.

In this study, “study treatment” refers to the combination of all study treatment components.

2.2 EFFICACY OBJECTIVES

Response will be determined through use of the PET-CT scans or CT scans alone, using Revised Lugano Response Criteria for Malignant Lymphoma (Cheson et al. 2014; see Appendix 3), hereinafter referred to as Lugano 2014 criteria. Response will be determined by an Independent Review Committee (IRC) and by the investigator.

2.2.1 Primary Efficacy Objective

The primary efficacy objective for this study is to evaluate the efficacy of induction treatment with Atezo+G+Len on the basis of the following endpoint:

- CR at EOI as determined by the IRC on the basis of PET-CT scans

2.2.2 Secondary Efficacy Objectives

The secondary efficacy objective for this study is to evaluate the efficacy of induction and maintenance treatments with Atezo+G+Len on the basis of the following endpoints:

- CR at EOI as determined by the investigator on the basis of PET-CT scans
- CR at EOI as determined by the IRC and by the investigator on the basis of CT scans alone

- Objective response (defined as a CR or PR) at EOI as determined by the IRC and by the investigator on the basis of PET-CT scans
- Objective response (defined as a CR or PR) at EOI as determined by the IRC and by the investigator on the basis of CT scans alone
- Best response of CR or PR during the study as determined by the investigator on the basis of CT scans alone

2.2.3 Exploratory Efficacy Objectives

The exploratory efficacy objective for this study is to evaluate the long-term efficacy of Atezo+G+Len on the basis of the following endpoints:

- For patients who have positive PET scans at EOI: CR at 12 months as determined by the IRC and by the investigator on the basis of PET-CT scans
- PFS, defined as the time from initiation of study treatment to first occurrence of disease progression or relapse, as determined by the investigator on the basis of CT scans alone or death from any cause
- Event-free survival (EFS), defined as the time from initiation of study treatment to any treatment failure, including disease progression or relapse, as determined by the investigator on the basis of CT scans alone; initiation of new anti-lymphoma therapy; or death from any cause, whichever occurs first
- Disease-free survival (DFS), defined as the time from the first occurrence of a documented CR to relapse among patients achieving a CR, as determined by the investigator on the basis of CT scans alone or death from any cause, whichever occurs first
- Duration of objective response (DOR), defined as the time from the first occurrence of a documented objective response to the time of disease progression or relapse, as determined by the investigator on the basis of CT scans alone or death from any cause, whichever occurs first.
- Overall survival (OS), defined as the time from initiation of study treatment to death from any cause

2.3 PHARMACOKINETIC OBJECTIVE

The PK objective for this study is to characterize the pharmacokinetics of atezolizumab, obinutuzumab, and lenalidomide, when given in combination, on the basis of the following endpoints:

- Observed serum obinutuzumab concentration at specified timepoints
- Observed serum atezolizumab concentration at specified timepoints
- Observed plasma lenalidomide concentration at specified timepoints

2.4 IMMUNOGENICITY OBJECTIVES

The immunogenicity objective for this study is to evaluate the immune response to obinutuzumab and to atezolizumab on the basis of the following endpoints:

- Incidence of human anti-human antibodies (HAHAs) to obinutuzumab during the study relative to the prevalence of HAHAs at baseline
- Incidence of anti-therapeutic antibodies to atezolizumab during the study relative to the prevalence of anti-therapeutic antibodies at baseline

The exploratory immunogenicity objective for this study is to evaluate potential effects of HAHAs or anti-therapeutic antibodies on the basis of the following endpoint:

- Correlation between HAHA or anti-therapeutic antibody status and efficacy, safety, or PK endpoints

2.5 BIOMARKER OBJECTIVE

The exploratory biomarker objective for this study is to identify non-inherited biomarkers that are predictive of response to study treatment (i.e., predictive biomarkers), are associated with progression to a more severe disease state (i.e., prognostic biomarkers), are associated with acquired resistance to study treatment, are associated with susceptibility to developing adverse events, can provide evidence of study treatment activity, can increase the knowledge and understanding of lymphoma biology or study treatment mechanism of action, or can contribute to improvement of diagnostic assays, on the basis of the following endpoint:

- Association between non-inherited biomarkers (listed in Section 4.5.7) and efficacy, safety, PK, or immunogenicity endpoints

3. STUDY DESIGN

3.1 DESCRIPTION OF STUDY

3.1.1 Overview of Study

This Phase Ib/II, open-label, multicenter, non-randomized, dose-escalation study will evaluate the safety, efficacy, pharmacokinetics, and immunogenicity of Atezo+G+Len in patients with relapsed or refractory FL. The study will include an initial dose-escalation phase designed to determine the RP2D for lenalidomide in this treatment combination (see Section 3.1.2) followed by an expansion phase in which lenalidomide will be given at the RP2D (see Section 3.1.3). All patients will receive induction treatment with Atezo+G+Len for six cycles. Patients achieving a CR, a PR, or stable disease at EOI will be eligible to receive extended dosing of Atezo+G+Len as maintenance treatment (refer to Sections 3.1.2.2 and 3.1.3 for details on treatment regimens). A study schema is provided in Figure 1.

Overall, it is planned to have approximately 46 patients enrolled in this study at approximately 15 investigative sites around the world, mainly in Europe and North America.

All patients will be closely monitored for adverse events throughout the study and for at least 35 days after the last dose of study treatment (see Section 5.3.1). Adverse events will be graded according to the National Cancer Institute Common Terminology Criteria for Adverse Events (NCI CTCAE) v4.0. An Internal Monitoring Committee (IMC) will be established to monitor patient safety throughout the study (see Section 3.1.4).

To characterize the PK properties of obinutuzumab, atezolizumab, and lenalidomide as well as the immunogenicity of obinutuzumab and atezolizumab when given in combination, blood samples will be taken at various timepoints before and during dosing (see Appendix 2).

Response will be determined by the IRC (see Section 3.1.5) and the investigator using the Lugano 2014 criteria (see Appendix 3). The primary efficacy endpoint will be based on IRC assessment of response. Refer to Section 4.5.5 for details on tumor assessments.

During induction treatment, all patients will have a CT scan performed at the end of Cycle 2 to confirm absence of early disease progression. Because of the potential for tumor flares with immunotherapies, which result in early apparent radiographic progression (pseudoprogression/tumor immune infiltration), including the appearance of new lesions followed by delayed response (Wolchok et al. 2009), patients whose CT scans meet criteria for disease progression may continue to receive study treatment at the discretion of the investigator and following discussion with the Medical Monitor if a moderate increase is seen in one lesion only or if at least two of the following criteria are met:

- Absence of symptoms and signs, including worsening of laboratory values (e.g., increased LDH) that indicate unequivocal disease progression
- No decline in Eastern Cooperative Oncology Group (ECOG) Performance Status
- Absence of tumor progression at critical anatomical sites (e.g., leptomeningeal disease) that cannot be managed by protocol-allowed medical interventions

Patients with radiographic evidence of progression at the end of Cycle 2 who continue to receive study treatment per the above criteria should have a CT scan repeated 4–8 weeks later.

3.1.2 Dose-Escalation Phase

The purpose of the dose-escalation phase is to identify the RP2D for lenalidomide when combined with fixed doses of obinutuzumab and atezolizumab as induction treatment (see Section 3.3.1).

Approximately 6–12 patients will be enrolled in the dose-escalation phase. Dosing groups of 3–6 patients each will be treated in accordance with the treatment regimens and the dose-escalation rules described in Section 3.1.2.2.

Patients will be closely monitored for adverse events during a DLT assessment window, defined as Cycle 2. Adverse events meeting the criteria for DLT, as defined below (see Section 3.1.2.1), will be reported to the Sponsor within 24 hours (see Section 5.4.2).

Patients who discontinue from the study prior to completing the DLT assessment window for reasons other than a DLT will be considered non-evaluable for dose-escalation decisions and for RP2D assessments and will be replaced by an additional patient at that same dose level. Patients who miss one or more doses of atezolizumab or obinutuzumab or five consecutive daily doses of lenalidomide during the DLT assessment window for reasons other than a DLT will also be replaced.

3.1.2.1 Definition of Dose-Limiting Toxicity

In this study, a DLT is defined as any one of the following events occurring during Cycle 2 of treatment and assessed by the investigator as related to study treatment:

- Adverse event of any grade that leads to a delay of more than 14 days at the start of the next treatment cycle
- Hematologic adverse event that meets any of the following criteria:
 - Grade 3 or 4 neutropenia in the presence of sustained fever of $> 38^{\circ}\text{C}$ (lasting > 5 days) or a documented infection
 - Grade 4 neutropenia lasting > 7 days
 - Grade 3 or 4 thrombocytopenia that results in significant bleeding per investigator judgment
 - Grade 4 thrombocytopenia lasting > 7 days
- Grade 3 or 4 non-hematologic adverse event, with the following exceptions:
 - Grade 3 or 4 IRRs
 - Note that IRRs may occur even after a small amount of drug has been administered (i.e., IRRs are not dose dependent).
 - Grade 3 diarrhea that responds to therapy within 72 hours
 - Grade 3 nausea or vomiting that occurs in the absence of premedication and responds to adequate therapy within 72 hours

Other toxicities occurring during Cycle 2 that are considered to be clinically relevant and related to study treatment, as determined by the investigator and the Medical Monitor, may also be considered DLTs.

3.1.2.2 Treatment Regimens and Dose-Escalation Rules

A 3+3 dose-escalation schema will be used. Induction treatment will be administered in 28-day cycles, as outlined in Table 1. Obinutuzumab and atezolizumab will remain at fixed doses during the dose-escalation phase. For induction treatment, the starting dose for lenalidomide is 15 mg, which is one dose level below 20 mg, the RP2D identified for lenalidomide when given in combination with obinutuzumab in a Phase Ib/II study

(MO28005 [GALEN]). If the 15-mg dose is safe and tolerable, the lenalidomide dose will be escalated to 20 mg. Inpatient dose escalation is not allowed.

Table 1 Induction Treatment for Dose-Escalation Phase

Cycle(s)	Atezo+ G +Len (28-Day Cycles)
1	
 • Lenalidomide 15 or 20 mg^a PO once daily on Days 1–21 • Obinutuzumab 1000 mg IV on Days 1, 8, and 15
2–6	
 • Lenalidomide 15 or 20 mg^a PO once daily on Days 1–21 • Obinutuzumab 1000 mg IV on Day 1 • Atezolizumab 840 mg IV on Days 1 and 15

IV=intravenous; PO=by mouth.

^a Dose may be de-escalated to 10 mg.

Dose escalation will occur in accordance with the rules listed below.

First Dosing Group (15 mg of Lenalidomide)

- A minimum of 3 patients will initially be enrolled in the first dosing group (15 mg of lenalidomide). Patients within the dosing group may be treated in parallel.
- If none of the first 3 DLT-evaluable patients experiences a DLT, enrollment of the second dosing group (i.e., 20 mg of lenalidomide) may proceed.
- If 1 of the first 3 DLT-evaluable patients experiences a DLT, the dosing group will be expanded to at least 6 patients. If there are no further DLTs in the first 6 DLT-evaluable patients, enrollment of the second dosing group may proceed.
- If 2 or more of the first 3 DLT-evaluable patients experience a DLT, the RP2D will have been exceeded, and dose escalation will stop. The Medical Monitor, in discussion with the Principal Investigator and participant investigators, may decide to proceed with dose de-escalation and enroll patients at 10 mg of lenalidomide, following the same 3+3 design.
- If 2 or more of the first 6 DLT-evaluable patients experience a DLT, the RP2D will have been exceeded, and dose escalation will stop. The Medical Monitor, in discussion with the Principal Investigator and participant investigators, may decide to proceed with dose de-escalation and enroll patients at 10 mg of lenalidomide, following the same 3+3 design.

Second Dosing Group (20 mg of lenalidomide)

- A minimum of 3 patients will initially be enrolled in the second dosing group (20 mg of lenalidomide). Patients within the dosing group may be treated in parallel.
- If none of the first 3 DLT-evaluable patients experiences a DLT, the dosing group will be expanded to 6 patients to confirm the dose of 20 mg as the RP2D for lenalidomide.

- If 1 of the first 3 DLT-evaluable patients experiences a DLT, the dosing group will be expanded to at least 6 patients. If there are no further DLTs in the first 6 DLT-evaluable patients, 20 mg will be declared the RP2D for lenalidomide.
- If 2 or more of the first 3 DLT-evaluable patients experience a DLT, the RP2D will have been exceeded, and 15 mg will be declared the RP2D for lenalidomide.
- If 2 or more of the first 6 DLT-evaluable patients experience a DLT, the RP2D will have been exceeded, and 15 mg will be declared the RP2D for lenalidomide.

The highest dose at which <33% of the DLT-evaluable patients (i.e., fewer than 2 of 6 patients) experiences a DLT will be declared the RP2D for lenalidomide that will be used in the expansion phase.

On the basis of a review of real-time safety data and available preliminary PK data, dose escalation may be halted or modified by the Sponsor as deemed appropriate.

Relevant demographic, adverse event, laboratory, and PK (if available) data will be reviewed prior to dose-escalation decisions, by the Medical Monitor in consultation with the Principal Investigator and participant investigators.

Although the DLT assessment window is defined as Cycle 2, cumulative toxicities occurring beyond Cycle 2 may be considered when determining the RP2D.

Patients who achieve a CR, a PR, or stable disease at EOI may receive maintenance treatment with Atezo+G+Len, as outlined in [Table 3](#). Maintenance treatment should start 8 weeks (\pm 1 week) after Day 1 of Cycle 6 and will continue until disease progression or unacceptable toxicity for up to 24 months.

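### If 15 mg has 0/3 DLTs and 20 mg then fails, 15 mg can be declared the RP2D on as few as three DLT-evaluable patients, although 20 mg needs six

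*Combined protocol and SAP*

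**What the plan says.** All the rules are in section 3.1.2.2.

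- **15 mg.** At least three patients are enrolled. "If none of the first 3 DLT-evaluable patients experiences a DLT, enrollment of the second dosing group" (20 mg) may proceed. With 1/3 DLTs the group grows to at least six, and 20 mg opens if there is no further DLT. With two or more DLTs in three or six, escalation stops, and the Medical Monitor, in discussion with investigators, may choose to "enroll patients at 10 mg of lenalidomide, following the same 3+3 design".
- **20 mg.** After 0/3 DLTs, "the dosing group will be expanded to 6 patients to confirm the dose of 20 mg as the RP2D for lenalidomide". After 1/3 it is also expanded to at least six. With two or more DLTs in the first three or the first six, the RP2D has been exceeded, "and 15 mg will be declared the RP2D for lenalidomide".
- **Summary criterion.** The RP2D is "The highest dose at which <33% of the DLT-evaluable patients (i.e., fewer than 2 of 6 patients) experiences a DLT".
- **Discretion.** "cumulative toxicities occurring beyond Cycle 2 may be considered when determining the RP2D", and "dose escalation may be halted or modified by the Sponsor as deemed appropriate". Section 3.1.4 has the Internal Monitoring Committee (IMC) review the data behind the RP2D.

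Section 6.1 expects two dosing groups of 3–6 patients, 6–12 in total. Section 3.1.3 then treats about 40 expansion patients at the RP2D and pools them with escalation patients who received that dose.

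**The concern.** The two doses are held to different standards. At 20 mg a clean group of three is not enough, and three more patients are required to confirm the dose. At 15 mg a clean group of three can become the RP2D with no further patient. The gloss of fewer than 2 of 6 cannot be applied to a group of three. If six patients at the RP2D were intended, no bullet puts that into effect for 15 mg, and the two 20 mg failure bullets point the other way.

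On this path, about 40 expansion patients would receive a dose whose DLT evidence for the three-drug combination is three patients, after the next dose up has failed the rule. The doublet experience ("Eighty-eight patients with relapsed/refractory FL were evaluable for safety and 86 for efficacy", section 1.4.3.2) is reassuring. It is not triplet DLT evidence, because atezolizumab starts in Cycle 2, which is the DLT window. The section 6.11 triggers concern fatal and Grade 3–4 event rates, not the DLT limit that defines the RP2D.

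**Working it through.** **Inputs.** The rules come from section 3.1.2.2. The documents give no true DLT rates, so the rates below are assumptions. The 15 mg group is taken to enrol its minimum of three, and no discretionary step is used.

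**1. The plan's own figure.** In the 15/20 mg scheme, 15 mg clears with 3 patients (0/3) or 6 (1/3 then 1/6), and 20 mg uses 3 (two or more DLTs in three) or 6. Possible totals are 3+3 = 6, 3+6 or 6+3 = 9, and 6+6 = 12, which matches the stated 6–12. The total of 6 arises only when 15 mg has 0/3 and 20 mg fails in its first three, so the lower end of the plan's range is itself one of the paths at issue.

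**2. How often 15 mg rests on three patients.** Let p and q be the true DLT rates at 15 and 20 mg, and b(k) the binomial probability of k DLTs in 3 patients at rate p. The 20 mg dose fails with probability F = 1 − P(Bin(6,q) ≤ 1).

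- Declared on 3 patients: b(0)·F.
- Declared on 6 patients: b(1)·b(0)·F.
- Share on 3 patients: 1/(1 + b(1)), whatever q is.

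This share is 1/1.243 = 80% at p = 10% and 1/1.384 = 72% at p = 20%. It is never below 69%, because b(1) is at most 0.444 (at p = 1/3). Under these assumptions it is the usual way in which 15 mg becomes the RP2D.

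**3. Effect of a fill to six.** Values of F are 0.345 (q = 20%), 0.580 (30%), 0.642 (33%), 0.767 (40%) and 0.891 (50%).

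- Fill triggered: b(0)·F.
- Rejected once triggered: b(2) + b(3).
- 15 mg declared, current bullets: [b(0) + b(1)b(0)]·F.
- 15 mg declared, with fill: the line above minus b(0)[b(2) + b(3)]·F, which is the failed-fill probability.

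| Assumed 15/20 mg rates | Fill triggered | Rejected once triggered | 15 mg declared, now | 15 mg declared, with fill | Failed fill |
|---|---|---|---|---|---|
| 33%/40% | 23.1% | 25.5% | 33.3% | 27.4% | 5.9% |
| 40%/50% | 19.2% | 35.2% | 27.5% | 20.8% | 6.8% |
| 20%/33% | 32.9% | 10.4% | 45.5% | 42.1% | 3.4% |
| 20%/40% | 39.3% | 10.4% | 54.3% | 50.2% | 4.1% |
| 10%/30% | 42.3% | 2.8% | 52.5% | 51.4% | 1.2% |
| 10%/20% | 25.1% | 2.8% | 31.2% | 30.5% | 0.7% |

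Worked example at 33%/40%: b(0) = 0.67³ = 0.301, b(1) = 0.444, b(2) + b(3) = 0.255. Now: 0.301 × 1.444 × 0.767 = 0.333. Failed fill: 0.301 × 0.255 × 0.767 = 0.059. With fill: 0.333 − 0.059 = 0.274.

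**4. Precision.** One-sided 95% Clopper-Pearson upper bounds on the 15 mg DLT rate are 63% for 0/3, 58% for 1/6 and 39% for 0/6.

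**5. Maximum size.** Today it is 6 + 6 = 12 evaluable patients. With a fill, 15 mg and 20 mg could each use six and fail, and 10 mg could then use six: 6 + 6 + 6 = 18.

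**The case against.** The strongest reply is that this is ordinary 3+3 practice. A result of 0/3 is below 33%, three-patient groups are within the plan, and a dose that just passes with 1/6 has an upper bound of 58%, little better than 63%. The minimum of three allows more to be enrolled, later toxicity may be weighed, the Sponsor may modify escalation, and the IMC reviews the RP2D data. All of that stands and keeps the point small. None of it, however, sets a minimum number of patients at 15 mg.

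Prior evidence also counts against high DLT rates at 15 mg, where a fill helps most. That dose is one level below the doublet's recommended 20 mg. Section 1.3.2.1 reports no DLTs for single-agent atezolizumab among 629 patients, section 3.3.2.1 reports safe use of atezolizumab with obinutuzumab in the first six DLT-evaluable patients, and section 5.1.4 expects very little added haematologic toxicity. This is relevant, but none of it is DLT evidence for the triplet.

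A reader might infer that failure at 20 mg shows 20 mg to be too toxic, and so makes 15 mg suspect. The rules do not support that. Failure needs only 2 of 6 DLTs, and at a true 20 mg rate of 20% the rule still fails the dose 34% of the time (F = 0.345). At assumed rates of 10%/20%, the fill is triggered in 25% of trials and rejects 15 mg in 2.8% of those. In the rest it only adds a pause.

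**Conclusion.** The gap is real and follows from the text without any assumed rate: 15 mg can be declared on as few as three DLT-evaluable patients, while the same section asks for six to confirm 20 mg. A fill to six would apply the plan's own confirmation standard to the dose that the expansion patients receive.

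The benefit is modest. It is about 6 to 7 points fewer declarations of 15 mg when its assumed DLT rate is 33% or 40%, against 3 to 4 points more loss of a tolerable dose at 20% and about 1 point or less at 10%. A rate of 33% lies at the plan's limit, so 40% is the clearer example of a dose that should be rejected. These sizes rest wholly on assumed rates.

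A reader might also infer that the plan breaks its own RP2D limit or contains a statistical error. It does neither: 0/3 satisfies the literal criterion, and the stated 6–12 is consistent with the bullets. This is a low-cost safety improvement to consider, not a fatal gap.

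**What to change.** Make the change within the dose-escalation phase. Section 3.1.2 replaces patients who are not DLT-evaluable only there, and sections 3.1.1 and 3.1.3 define expansion as treatment at an RP2D already chosen. Amend the two 20 mg failure bullets to read:

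*If fewer than 6 DLT-evaluable patients have been treated at 15 mg, the 15 mg dosing group will be expanded to 6 DLT-evaluable patients before the expansion phase opens. 15 mg will be declared the RP2D only if at most 1 of 6 has a DLT; otherwise the existing discretionary de-escalation to 10 mg applies.*

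State also that any dose declared the RP2D, including 10 mg, needs six DLT-evaluable patients with at most one DLT. Otherwise the same gap reappears at 10 mg. Add a caveat to the 6–12 statements (synopsis, sections 3.1.2 and 6.1) and to the totals of about 46 (synopsis, section 3.1.1): escalation could reach 18 evaluable patients if 10 mg is opened after 15 mg and 20 mg fail. With about 40 in expansion, that is about 58.

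**Cost.**
- Up to three more patients in escalation, pooled with expansion if 15 mg is declared.
- About 8 weeks' delay after the last of them starts (two 28-day cycles), or up to about 10, because a DLT includes a delay of more than 14 days in starting the next cycle.
- The small added loss of a tolerable 15 mg dose given above.
- A possible 10 mg group in about 3% to 7% of trials at assumed 15 mg rates of 20% to 40%, with one or two further DLT windows.

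If the Sponsor prefers no fill, a one-line justification in section 3.1.2.2 for accepting three patients at 15 mg would answer the point.
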